### **Summary of Significance**

AYAs with chronic conditions remain more dependent on their parents and health care providers than their healthy peers, and lack independence in activated self-management. This over-reliance on parents and health care providers often impedes developing the independence necessary for successful transition to young adulthood and adult health care services. There is a lack of scalable, theoretically guided interventions that build the capacity of AYAs to develop and implement chronic condition activated self-management behaviors. Non-directive peer coaching, delivered using an informatics-based platform, can promote intrinsic motivation and is well suited to promote activated self-management in AYAs through the provision of social support in a format well-designed for engaging AYA.

### **3.C. Innovation**

Our Peer i-Coaching for Activated Self-Management Optimization (PICASO) intervention is innovative in several important ways.

1. First, it conceptually and practically couples **self-management skill development with patient activation**. Together, these two concepts synthesize the set of critical skills and motivations needed for the AYA to become engaged and effective managers of their chronic condition.
2. Second the PICASO intervention is designed to promote the development of activated self-management by AYAs with COCC using nondirective peer coaching. This novel approach provides AYAs with the opportunity to develop intrinsic motivation and competence to take control of their healthcare within the **nonjudgmental, nondirective environment established by a peer with a shared experience of living with a COCC**.
3. Third, **PICASO uses a proven informatics technology interface** (InquisitHealth Mentor 1:1™ Web Based Portal) that harnesses mobile technology to allow AYAs to be able to access their peer coach by phone or by text. Use of mobile technology to deploy the intervention decreases engagement barriers, allows AYAs from rural and urban areas and with varying schedules to participate, and employs a communication format that aligns with AYAs preferences for interpersonal interaction.
4. Fourth, **PICASO's technological innovation enhances scalability and allows for broad dissemination** across settings that serve AYAs such as schools, camps, or medical clinics. InquisitHealth Mentor 1:1™ Web Based Portal has been deployed commercially across multiple settings for peer support.

### **3.D. Approach**

**3.D.1 Overview.** We propose a 5-year mixed-methods, randomized controlled trial that tests the Peer i-Coaching for Activated Self-Management Optimization (PICASO) versus an attention control group in an academic health center setting.

**3.D.2.b. The PICASO was found to be feasible and acceptable and showed preliminary efficacy trends suggesting improvements in transition readiness and internal self-regulation.** Using a randomized controlled trial with a 3-month waitlist control group, we piloted PICASO in four of the sub-specialty ambulatory care clinics at Duke Children's Hospital. We enrolled 25 AYAs, 16 to 22 years, over a 9-month period (Intervention N=13; Wait-list control N=12) from four diagnostic categories: cancer (N=6), inflammatory bowel disease (N=6), lupus (N=7), sickle cell disease (N=6). The attrition rate at month 3, 23% in the intervention group and 25% in the wait-list control group, was consistent with that reported in other adolescent clinical trials. Reasons for withdrawal following randomization included: time constraints (n=3), medical crisis (n=1), unable to contact (n=1), and difficulty completing surveys due to low cognitive ability (n=1). Content analysis of post-intervention completion interviews supported high acceptability and satisfaction with PICASO. Themes with data samples included: Shared Experiences (e.g., "He was just.. I can't even explain it in words...but just he was also a fellow Hodgkin's survivor so just kind of having that connection and just having someone there. He was very encouraging and that was very meaningful to me."); Motivation Sharing (e.g., "I knew that I had this goal. She gave me motivation to get up and pursue it."); Progress Towards Goals (e.g., "I definitely feel like we accomplished a lot. A lot in a little bit of time."); Usefulness of Coaching (e.g., "I think that it's something that every cancer patient needs because you know you're just looking at having cancer and your like, okay I just got through this but life goes on after having cancer so this was really a big part of putting that into perspective."). Clinically meaningful improvement for outcomes was defined as a median baseline to month 3 improvement per AYA of 5% or greater for the group. We found clinically meaningful improvement in transition readiness in the intervention group but not in the control group (median improvement 7.5% vs 3.9% respectively). Clinical improvement was also found in intentional self-regulation in both the intervention and waitlist control groups (median improvement 14.3% vs 12.5% respectively). A clinically meaningful improvement on the Patient Activation Measure (PAM) has been defined in previous studies as a 2-point or greater increase. Among the 19 participants (10 intervention, 9 controls) who completed the 3-month assessment, a clinically significant improvement was observed in five (50%) of those receiving the intervention and five( 55.6%) of those in the waitlist control group.

### 3.D.3 Experimental Approach

#### 3.D.3.a. Overview of aims, design, analyses, and timeline (Table 3).

Aims	Design & participants	Analyses
Aim 1: Test efficacy of PICASO versus attention control group on primary and secondary outcomes across 12 months	
 
Randomized controlled trial (RCT): 
 
AYA PICASO intervention group (N=150)
 
AYA attention control group (N=75)
 
 
 
Primary Outcomes: self-management and patient activation
 
Secondary Outcomes: transition readiness, health-related quality of life, emotional health
 
Assessments: baseline, 3,6,9,12 months
 
	Trajectory Analyses: Hierarchical mixed-effect models for longitudinal data with a posteriori comparisons at each assessment point to compare the trajectory of change in each outcome across 12 months in the PICASO intervention group compared to the attention control group
Aim 2: Explore moderating effects of AYA characteristics on primary and secondary outcomes across 12 months	
 
Same design and participants as above
 
Candidate baseline moderators: age, race/ethnicity, biological sex, type of chronic condition, and disease severity
 
	Exploratory Moderator Analyses: Trajectory analysis approach; Core trajectory model for each outcome as described in Aim 1 plus inclusion of each candidate moderator and its two-way and three-way interactions
Aim 3: Characterize user experiences with the intervention.	
 
Purposive stratified sample from RCT 
 
AYA PICASO intervention (n=50)
 
Post-intervention
 
 
 
	Mixed methods: Identify intervention responder typologies; identify themes

**3.D.3.b. Setting.** The 12-month PICASO intervention will be tested at the Duke Children's Health Center, a large multi-specialty ambulatory children's hospital caring for over one thousand AYAs each year with a range

of COCC. Co-PI [name] has successfully recruited over 170 youth through the Duke Children's Health Center for other studies and has dedicated support from each of the clinics that would serve as recruitment sites. Based on these and other prior recruitment efforts by both Co-PIs, we anticipate that 70-80% of youth approached will consent to participate with a 90% retention rate.

**3.D.3.c. Description of study population.** The usefulness of diagnostic groupings in studies of chronic condition self-management has been called into question since the landmark studies conducted by Stein, Jessup and colleagues. Since then, a range of studies on adaptation to COCC have supported the view that there is more variability within diagnostic groupings than between, suggesting that diagnosis is not a helpful categorization in the examination of adaptation. The only area in which differences are found is family interaction with the health system. Considering these findings, and our focus on outcomes that are not disease-oriented, we have adopted a modified noncategorical approach to defining the population. The list of chronic conditions included in this study is broad and includes conditions that require frequent hospital-based treatment (sickle cell disease, chronic kidney disease, systemic lupus erythematosus), have specific daily management tasks and episodic periods of worsening/flare (type 1 diabetes, inflammatory bowel disease, severe asthma) and survivorship conditions in which participants have gone through some form of intense treatment and continue to deal with distressing symptoms and self-management tasks (stem cell transplantation, organ transplantation, childhood cancer survivor). For the purposes of peer coach matching, we created categories of chronic conditions based upon burden of condition attributed to chronicity and impairment (See Table 5). Peer coaches will be matched to AYAs based upon shared condition category. Eligibility criteria (detailed in [Human Subjects and Clinical Trials Information Section 2.2](#)) apply to participants in all Aims and are shown in Table 6.

**Table 5. Sample**

Condition Category	Diagnoses	N	Peer Coach
1. Frequent Hospitalizations or ED visits	Sickle Cell Disease; Chronic Kidney Disease, Lupus	50 PICASO 25 control	4-5
2. High daily management with intermittent flares	Type 1 Diabetes Mellitus; Inflammatory Bowel Disease; Severe Asthma	70 PICASO 35 control	5 -6
3. Survivor of life-threat condition requiring ongoing symptom mgmt	Stem Cell Transplant, Organ Transplant, Cancer Survivor	30 PICASO 15 control	3-4
Total: 150 PICASO / 75-control 2:1 ratio			12-15

**Table 6. Overview of eligibility criteria**

Inclusion
1. AYA 16 to 22 years
2. Childhood onset chronic condition from 1 of 3 condition categories (see Table Y).
3. Read and speaks English
4. Access to internet via computer or Smart Phone
4. Access to telephone (Smart Phone not required as text feature can be accessed via internet)
Exclusion
1. Diagnosed cognitive dysfunction
2. Need for English translator

**3.D.3.d. Outcome measures.** Study outcomes are described in detail in [Human Subjects and Clinical Trials Information Section 4.3](#). All outcomes have been piloted by our team and chosen based on the conceptual model, expert recommendations, and psychometrics. Response burden will be minimized with short instruments and online data entry via REDCap survey. Pilot testing confirmed completion times ranging from 15-20 minutes.

Primary outcome measures. The constructs of (a) self-management and (b) patient activation will be assessed at baseline, 3-, 6-, 9-, and 12-months post randomization. Self-management will be measured using the Partners in Health Scale (PIH), assessing chronic condition self-management knowledge, partnership in treatment, recognition and management of symptoms, and coping. Patient activation will be measured using the Patient Activation Measure (PAM). The PAM measures patient activation through self-reports of knowledge, skills, and confidence related to self-management of one's own health care.

Secondary outcome assessments. The following constructs will be assessed as secondary outcomes at baseline, 3-, 6-, 9-, and 12-months post randomization: (a) transition readiness, (b) health related quality of life, and (c) emotional health. Transition readiness will be measured by the Transition Readiness Assessment Questionnaire (TRAQ). The TRAQ assesses transition readiness in youth with COCC in domains of self-advocacy (communication and use of resources in the community and school) and chronic disease self-management (scheduling appointments, asking questions of health care providers, filling prescriptions). Health related quality of life will be measured using the Short-Form 12 (SF-12) which produces weighted subscales on physical and mental components of quality of life. Emotional health will be measured using the Brief Symptom Inventory (BSI) which assesses emotional symptom experience (depression, anxiety, somatization) over the previous week.

**3.D.3.e. Data management plan for all aims.** [Human Subjects and Clinical Trials Information Sections 3.1.b. & 3.3.3](#) detail data management and security. Briefly, all study data will be entered by participants and the

study Clinical Research Coordinator (CRC) via REDCap data system residing on a Duke University RHEL Server. Leveraging a unique password system, only the Study Manager will be unblinded to study group in the data system. Weekly reports will be reviewed to monitor enrollment, retention, safety, and missing data.

### **3.D.4.a. Study Procedures by Specific Aim**

**Aim 1:** Determine the efficacy of the PICASO on primary outcomes (self-management, patient activation) and secondary outcomes (transition readiness, health-related quality of life, emotional health) across 12 months.

**Aim 2:** Explore moderators of trajectory of PICASO effects on self-management, patient activation, transition readiness, health-related quality of life and emotional health across 12 months.

Overview and design: We will test the hypothesis that compared to an attention control group, the PICASO group will improve self-management and patient activation as well as improve secondary outcomes (transition readiness, HRQoL, emotional health) in a RCT over 12-months with 225 AYAs with COCC. The primary outcomes are the post-intervention scores on the Partners in Health Scale and the Patient Activation Measure.

Recruitment plan: Our detailed Recruitment and Retention Plan is provided in [Human Subjects and Clinical Trials Information Section 2.5](#); a brief summary follows. Participants will be recruited by the study CRC in partnership with the Duke Children's Health Center ambulatory clinic staff (attending physicians, fellows, and nurse practitioners - see Letters of Support from Clinic Medical Directors). At the end of each week clinic staff and the CRC will review lists of AYAs scheduled for appointments the following week. Eligible AYA will be identified and flagged to be provided with basic information about the study by the clinic staff the following week. If an AYA and parent/guardian (for those less than 18 years) express an interest in the study, the CRC will meet with them at the same appointment for study introduction. Once questions have been answered the informed consent process will be conducted by the CRC in a confidential manner.

Randomization and data collection (detail in [Human Subjects and Clinical Trials Information Section 4.2.a.7 & 4.2.a.11](#)): On completion of baseline data collection, AYAs will be randomized using a stratified randomization with permuted block sizes of four to either the PICASO intervention (N=150) or attention control group (N=75). While stratifying on condition category, a 2:1 treatment allocation will be applied to ensure as an intervention sample size that is sufficient to provide robust findings and increase the precision of the outcome parameter estimates for the PICASO intervention. A RedCAP data base platform will be used to administer the randomization scheme prepared by the study statistician.

Peer coach recruitment and training ([details in Human Subjects and Clinical Trials Information Sections 4.3.a](#)): Peer coaches are young adults (18-26 years) with a COCC who have been identified by clinic staff (attending physicians, fellows, nurse practitioners) as having exemplary activated self-management skills and, based upon their interpersonal skills, having the potential to be trained as a peer coach. Those young adults who are recommended will undergo a screening process and interview by the study investigators ([name], [name], [name]). If they express interest in training and employment as a peer coach they will be hired and trained following the training protocol described below. We plan to employ 12- 15 peer coaches who represent the condition categories (see Table 5). Peer coaches will receive training from Co-I [name] (Coach Supervisor) using a health and wellness curriculum designed by [name] who is an Integrative Health Coach, and previously tested by the study investigators. Training is composed of a five-day program and ongoing semi-monthly supervisory sessions. Training content includes a review of the coaching framework including social support and self-determination theories, motivational interviewing techniques and information about health behavior change. Training sessions focus on the coach-AYA relationship and use of motivational interviewing techniques. Various role-playing sequences are used throughout the training program to provide coaches with the opportunity to test their skills. Semi-monthly supervisory sessions will be conducted with coaches and the research team including continued education and support. Supporting AYAs with a similar condition as oneself can be emotionally distressing at times, and both [name] who is a licensed pediatrician and pediatric psychiatrist, and [name], LCSW who is a licensed clinical social worker, can consult and refer coaches experiencing problems.

[figure not shown]
Peer i-Coaching for Activated Self-Management Optimization (PICASO) ([details in Human Subjects and Clinical Trials Information Sections 4.2.a.12-15](#)): The PICASO intervention is a peer coaching intervention based upon self-determination theory. The intervention is delivered by young adults (18-26 years) with a COCC and trained using a tested curriculum that includes motivational interviewing techniques and the benefits of peer relationships over a shared experience such as a COCC. The peer coach supports the AYA to identify their own goals and feel a sense of success in making change towards goals within a supportive environment. This peer-centric process involves goal-setting, the development of self-discovery and provides accountability for changes in health behavior. The peer coach elicits the AYA's vision of optimal health and identifies the AYAs values; both necessary for behavior change. As the AYAs identify a vision of wellness and

develop goals and action steps to progress towards that vision, the peer coach elicits the AYA's intrinsic motivation and activates skill development in self-advocacy and communication and empowers the AYA to take leadership in managing their condition.

Peer coaching is tailored to the AYA's developmental level and designed to address the four key functions of peer support that have been found to be associated with increased self-management: 1) participation in daily management, 2) support for social and emotional issues, 3) linkage to clinical care, and 4) ongoing support. The peer coaches work consistently over time, using nondirective approaches, to guide the AYA to address goals around daily management, navigation of the health care system, communication with health care providers, and emotional coping.

Figure 2 identifies characteristics of the AYA that are known to be related to the development of independent self-management. The intervention is designed to address a range of these characteristics and to have flexibility to support AYAs based on known variations. For example, the intervention can be tailored so that younger AYAs receive support targeting earlier stages of the development of activation and self-management. Each AYA will be matched with a coach, based on membership in 1 of 3 condition categories (see Table 5), who will provide support using the InquisitHealth Mentor 1:1™ Web Based Portal mobile telephone/text platform and the curriculum that guides them to assess AYA goals and provide support in addressing these goals.

To enact the four key functions of peer support, the coaches develop a relationship over time with their assigned AYAs. The first phase of the intervention involves an assessment and goal setting call during which the peer coach learns about the AYA's experience with their COCC, how they view their current self-management skills and how they envision their ideal health in adulthood. Through this initial call the coach and AYA will identify specific goals to work towards their vision of health. Throughout the process of coaching, the coach and AYA identify action steps towards the health and self-management goals, draw upon the AYA's strengths and existing skills, examine potential barriers to successful progression towards their goals and develop plans for addressing those barriers. The curriculum for the intervention is nondirective but allows coaches to help AYAs identify areas to work on within the four domains of self-management – knowledge, partnership in treatment, recognition/management of symptoms, and coping – as they relate to the AYA's personal health goals and vision for their future. Table 1 provides examples of the ways in which a peer coach would provide support to an AYA participant utilizing a nondirective approach.

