In general, calls last 20-30 minutes. During the first call, the coach and AYA have the opportunity to learn about one another's experiences with living with a chronic condition. During subsequent calls, the coach focuses primarily on the specific sub-behavior elected by the AYA. The coaching process model described in figure 2, helps the coach guide behavior change, beginning with assessing the participant's vision for the future, establishing focus, readiness to change, and then pursuit and maintenance of identified goals. As goal progress is made, the coach and AYA work to identify a new goal, or in the case of no progress, they discuss barriers and strategies, with an option to move on to another goal. Between sessions the coach and participant can exchange text messages including an update on progress towards a goal. At the end of the intervention the final call involves an opportunity for closure and for the coach and AYA to review progress on goals and future steps.

Attention Control: Over 12 months the attention control group participants will receive a monthly electronic newsletter with educational content about COCC management and the differences between pediatric and adult health care systems, as well as a monthly phone call from study staff to ensure receipt of the newsletter and to answer questions regarding content, and an opportunity to link them to other resources. If participants report health concerns they will be directed to contact their health care team.

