personalization, replicability, and scalability. Interview transcripts will be analyzed using a content qualitative analysis technique that combines structural (e.g., intervention component, transition barriers) and magnitude coding (e.g., theme intensity) with inductive coding (e.g., variations in outcomes not captured by instruments). Drs. [name] and [name] will separately code 10 interviews, discuss the generated codes, and create an initial code book by consensus. The code book will then be used by CRC coders for the next 10 transcribed interviews (with [name] coding each 5th interview), with further refinements made as needed. The final code book will be organized into categories used to generate themes of mechanistic and process elements. The qualitative content analysis findings within each case will then be integrated with the relevant quantitative questionnaire- and informatics-based data. A matrix will be constructed to display case findings (qualitative data in relation to quantitative data) in relation to every other case. This will allow a cross-case comparative analysis, with the possibility of conducting an even wider range of theoretically driven analyses. For example, case comparisons could be made by diagnostic category or mentor condition match. Next, process tracing will be used to explore how particular case outcomes (e.g., self-management, coping, self-esteem) may have been related to intervention components (e.g., goal selection, strategies). [name] will use ATLAS.ti software to aid in coding and organizing transcribed interviews and field notes.

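### One fixed block size of four, in three strata at one site, could let recruiting staff who learn past assignments deduce up to 33–44% of assignments; undisclosed, varying blocks in multiples of three would cut this to about 4%

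*Combined protocol and SAP*

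**What the plan says.** All references are to the combined protocol and SAP.

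- **Randomization (3.D.4.a, Randomization and data collection).** After baseline data collection, participants are allocated by "stratified randomization with permuted block sizes of four". The same paragraph adds: "While stratifying on condition category, a 2:1 treatment allocation will be applied". The targets are 150 PICASO and 75 control. REDCap runs a list prepared by the study statistician. No second block size is mentioned, and nothing says the size is withheld from recruiters.
- **Strata and site.** Table 5 gives three condition categories with planned totals of 75 (50/25), 105 (70/35) and 45 (30/15). Section 3.D.3.b names one centre.
- **Recruitment (3.D.4.a, Recruitment plan).** Each week "clinic staff and the CRC will review lists of AYAs scheduled for appointments the following week". Eligible patients are flagged, clinic staff introduce the study, and the CRC sees those who are interested at the same appointment.
- **Masking (3.D.3.e).** The plan states that "only the Study Manager will be unblinded to study group in the data system".
- **Contact that reveals the arm.** "Each AYA will be matched with a coach, based on membership in 1 of 3 condition categories". The text after Table 7 lets coaches contact the clinical team, mainly over safety, and lets the team give coaches health information. Controls receive a newsletter "as well as a monthly phone call from study staff" (3.D.4.a, Attention Control).

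**The concern.** With a fixed, known block size, the end of each block can be worked out from the assignments already made in it. Concealing the list in REDCap protects future entries but not past ones, and past assignments can be learned in this trial without opening the data system. Participants know whether they have a coach. A clinic that exchanges information with a coach learns that the patient is in PICASO. Whoever makes the monthly calls knows that those people are controls.

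A recruiter who can predict the next arm can, knowingly or not, influence who is flagged or when someone is randomized. PIH and PAM are self-reported, and the intervention is meant to act through motivation. If readier patients were guided toward coaching, the result could resemble a treatment effect, and adjustment for baseline scores need not remove it.

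**Working it through.** **Inputs.** Block size 4, ratio 2:1, arms 150/75 (3.D.4.a); strata of 75, 105 and 45 (Table 5). The share of past assignments that recruiters learn, q, is not given, so it is an assumption ranging from 0 to 1.

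**1. The plan's own figure.** A block of four at 2:1 needs 4 × 2/3 = 2.67 PICASO places, which is not a whole number. Three-and-one blocks give 225 × 3/4 = 168.75 and 56.25. Two-and-two blocks give 112.5 and 112.5. Neither reproduces 150/75. Mixing two three-and-one blocks with one two-and-two block does average 2:1, since (3 + 3 + 2)/12 = 2/3, but the plan does not describe this. The block composition is therefore unknown, and each possibility is carried forward.

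**2. Full knowledge, fixed composition.** Once one arm of a block is used up, every remaining slot is certain, so the number of certain slots is the length of the final run. For a block with a PICASO and b control places its mean is a/(b+1) + b/(a+1).
- Two-and-two: 2/3 + 2/3 = 4/3; divided by 4, 33.3%.
- Three-and-one: 3/2 + 1/4 = 7/4; divided by 4, 43.8%.

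**3. Full knowledge, random mixture averaging 2:1.** In a three-and-one block only the last slot after three PICASO assignments is certain: 1/4 slot on average. In a two-and-two block the certain slots are those left after both controls are used: (2 + 1 + 1)/6 = 0.667. The share is [(2/3)(0.25) + (1/3)(0.667)]/4 = 0.389/4 = 9.7%. If the mixture were balanced within known sets of 12, enumeration gives 24.1%.

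**4. Partial knowledge.** Suppose each past assignment is seen independently with probability q, with block size and block starts known. Two-and-two gives q²/3; three-and-one gives 3q/8 + q³/16.

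| q | Two-and-two | Three-and-one |
|---|---|---|
| 1 | 33.3% | 43.8% |
| 0.75 | 18.8% | 30.8% |
| 0.5 | 8.3% | 19.5% |
| 0 | 0% | 0% |

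**5. Alternatives that fit 2:1, with full knowledge.**
- Fixed blocks of 3: (2/2 + 1/3)/3 = 44.4%.
- Fixed blocks of 6: (4/3 + 2/5)/6 = 28.9%.
- Sizes 3, 6 and 9 drawn at random: about 4%, by simulation at each stratum size. The simulated observer knows the three possible sizes but not which one is in use.

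Correcting the ratio alone, with fixed blocks of 3 or 6, therefore leaves most of the predictability in place.

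**6. Pace.** Section 3.C.10 shows accrual over 14 quarters, or 14 × 13 = 182 weeks. If accrual is even, the gap between randomizations in a stratum averages 182/105 = 1.7, 182/75 = 2.4 or 182/45 = 4.0 weeks. A block of four then fills in about 7 to 16 weeks.

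**The case against.** The strongest case against this point has five parts.

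- **Knowledge is not shown.** No passage says that recruiters are told the block size, and study group is masked in the data system. The routes are incomplete: coach–clinic contact reveals some PICASO patients to clinic staff, while the control calls are made by unspecified study staff, not stated to be the CRC. This stands, and is why 33% and 44% are upper limits. The masking is limited to the data system, however, and does not close the routes outside it.
- **Composition.** The random mixture would give about 10%. That also stands, but the plan does not describe a mixture.
- **Timing and discretion.** Randomization follows consent and baseline collection, so the next slot may change after a patient is approached, and no discretionary choice among eligible patients is described. This weakens the route without removing it. Lists are reviewed a week ahead, the CRC meets patients at the same appointment, the questionnaires take 15–20 minutes, and slots within a stratum are about 2 to 4 weeks apart on average.
- **Interview coding.** The Aim 3 plan says "The code book will then be used by CRC coders", which might look like another leak. Those interviews follow a 12-month intervention, far too late to reveal a block that fills in weeks. This route should not be counted.
- **Missing detail.** The plan refers to Human Subjects and Clinical Trials Information Sections 4.2.a.7 and 4.2.a.11, and to Section 2.5 for recruitment. None was supplied, so concealment provisions cannot be said to be absent.

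A reader might also infer that the trial is declared open-label. The documents do not say so; that participants know whether they have a coach follows from the nature of the intervention.

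**Conclusion.** The point holds in a conditional form. One fixed block size of four, in three strata at one centre, leaves an avoidable opening for selection bias. Recruiters who knew the block size and every past assignment in a stratum could deduce 33% (two-and-two) or 44% (three-and-one) of assignments. The share is 19–31% if three-quarters of past assignments are seen, 8–20% if half are seen, and about 10% under an undescribed random mixture with full knowledge.

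Two stronger readings are tempting and not supported. One is that staff will know a third or more of upcoming assignments for certain; that needs full knowledge and a fixed composition, and the documents establish neither. The other is that a particular inflation of the false-positive rate follows. That would need the amount and direction of any steering, which the documents do not give. The planned test is group-by-time in a random-coefficients model that includes baseline, so a constant level difference would largely drop out and steering linked to future change would be the main threat. No error rate should be quoted.

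**What to change.** - In section 3.D.4.a, replace the block size of four with randomly varying block sizes that are multiples of three, for example 3, 6 and 9. These also fit 2:1, so the same edit resolves the mismatch in step 1.
- Withhold the sizes and the list from the CRC and clinic staff. The protocol can say only that sizes vary in multiples of three, with the actual sizes in a restricted document.
- Lock the condition category in REDCap before the assignment is shown, so that the stratum cannot be changed once the arm is known.
- Make Human Subjects Sections 4.2.a.7 and 4.2.a.11 consistent with this.

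The cost is one protocol sentence and a regenerated REDCap list, with no extra staff. The small downside is that an incomplete last block may leave a stratum slightly off 2:1. With blocks of up to nine, the PICASO count can miss its target by at most two in a stratum (for example, six PICASO in the first six places instead of four).
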